If resection of fibroids and polyps does indeed improve reproductive performance, then this would have a potential influence on existing fertility pathways. For example, the NICE guidelines for fertility management suggest that IVF is the optimum treatment for women with unexplained infertility (25). Funding for IVF however is variable and inconsistent across the UK and is often limited to a single cycle. If women with submucous fibroids or polyps associated with unexplained infertility were to benefit from resection of these lesions, then in many cases IVF treatment could be avoided with consequent cost savings to both the NHS and to self-funding patients.–There is a current trend towards local authorities reducing funding for fertility treatments, thus increasing the burden on patients to fund this treatment themselves. Given this, and the emotional and medical side effects of receiving such treatments, it is imperative that evidence is created to guide clinicians and patients on the effects of hysteroscopic resection so that they can make an informed decision in relation to the patient's chances of live birth (30). There is therefore a current urgent need for a well-designed definitive study examining the effect of hysteroscopic resection of submucous fibroids and polyps in the two distinct populations of women with infertility and women with recurrent miscarriage, whether being managed expectantly or with active fertility interventions.

3. Aims and objectives

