13. Adverse events due to procedure related and gynaecological/obstetric related complications (see section 10)

Health Economics

14. Health resource use of the participant measured at baseline, 6, 15 and 24 months post randomisation.
15. Patient costs measured following hysteroscopy for participants randomised to hysteroscopic resection
16. Cost per live birth gained.

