The primary outcome analysis (the LBR at 15 months post-randomisation) may be affected by withdrawal or by women not receiving the randomised treatment allocation. That is if participants randomised to the intervention do not receive the resection by approximately 3-months post-randomisation we may not have a valid, reliable, and robust estimate of the effect of actually receiving the intervention. Rather we will just have an estimate of the policy of randomising participants to receive resection or not. Similarly, if participants randomised to the control treatment withdraw from the control treatment and receive a resection in the first 6-months post-randomisation then again we will not have a valid reliable and robust estimate of the effect of not receiving the intervention. If a substantial proportion of participants withdraw before 6 months post-randomisation or do not receive their treatment allocation by 3-post-randomisation then in these circumstances the comparison of the LBR outcome at 15 month post-randomisation outcome between the randomised groups may not produce a reliable and valid estimate of the effect of resection of fibroids / polyps or not.

The secondary outcome of time to live birth could also be affected by this. Statistical adjustment methods such as rank preserving structural failure time models and inverse probability weighting (IPCW) will be used to adjust for potentially informative withdrawal from randomised treatment (or withdrawal from the trial) in secondary analyses of the end of trial follow up data. These methods have been shown to perform well in a range of scenarios related to informative drop-out such as treatment crossover, though are associated with limiting assumptions (43–45). A subgroup analysis will include women with infertility/recurrent miscarriage. We also expect that IVF could be important and may differ between treatment arms. If this is the case we will undertake an analysis adjusting for IVF to estimate the relative effectiveness of surgery vs no surgery in the absence of IVF, using inverse probability of censoring weights.

Analysis of long term outcomes

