The primary cost-effectiveness analysis will present costs per extra live birth, comparing the surgical interventions to control taking an NHS and personal social services perspective in accordance with NICE guidelines (46). Extra live birth will be used as the outcome instead of quality adjusted life years (QALYs) because QALYs are intended to capture improvements in health, not for placing a value on additional lives (47), as recognised in the NICE Clinical Guideline for Fertility (25). Resource use will include the intervention costs for hysteroscopy, expectant management costs, costs of IVF/IUI treatments and for those who conceive antenatal and post-natal visits, delivery costs and any hospital stays not related to birth for both mother and baby. Patient centered costs related to time taken to travel to appointments to receive the intervention (and the loss of productivity associated with attending such appointments), non-NHS funded fertility treatments, and for those who conceive antenatal and post-natal visits will also be collected for use in a secondary analysis that will take a societal perspective. Women will be asked to complete a resource use questionnaire at baseline, 6, 15 and 24 months post randomisation – each questionnaire will ask for data from the preceding 3 months. Women in the hysteroscopy arms will be asked to complete a patient cost questionnaire following their hysteroscopy for information only relating to their hysteroscopy. Unit costs will be derived from appropriate national sources and will include NHS reference costs and Personal Social Service Research Unit costs (48,49). The resource use questionnaire will be designed for this study and will draw on data collection tools developed in SchARR and those collated by the Database for Instruments for Resource Use Measurement (DIRUM). Two sets of economic analyses will be conducted – one based on an intention-to-treat analysis of the trial data, and another based on an analysis that adjusts for potentially informative withdrawal of randomised treatment or trial withdrawal. Results will allow for uncertainty using bootstrapping and probabilistic sensitivity analysis.

12. Trial supervision

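### The secondary societal analysis counts patient travel and lost work time for resection visits but states none for fertility-treatment visits, so it misses that part of any difference in IVF use

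*Protocol*

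**What the plan says.** Section 11.2 (Health economic evaluation) sets a primary analysis from the NHS and personal social services perspective and a secondary one from a societal perspective.

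- **Counted in resource use, with no restriction by arm:** "Resource use will include the intervention costs for hysteroscopy, expectant management costs, costs of IVF/IUI treatments", followed by maternity and hospital costs.
- **Added for the societal analysis:** the cost of "time taken to travel to appointments to receive the intervention (and the loss of productivity associated with attending such appointments", and then "non-NHS funded fertility treatments, and for those who conceive antenatal and post-natal visits will also be collected for use in a secondary analysis".
- **Patient cost instrument:** "Women in the hysteroscopy arms will be asked to complete a patient cost questionnaire following their hysteroscopy for information only relating to their hysteroscopy". Section 8.3 lists the matching outcome as "Patient costs measured following hysteroscopy for participants randomised to hysteroscopic resection". Table 2 schedules this questionnaire once, directly after hysteroscopy.
- **Instrument for both arms:** a resource use questionnaire at baseline, 6, 15 and 24 months, where "each questionnaire will ask for data from the preceding 3 months". Its items are not listed.

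On IVF, section 2.1 says that if women with unexplained infertility benefited from resection, "in many cases IVF treatment could be avoided with consequent cost savings to both the NHS and to self-funding patients". Section 11.2, under intervention waiting times and withdrawal, says: "We also expect that IVF could be important and may differ between treatment arms".

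**The concern.** An incremental cost is undisturbed by leaving out an item only if that item is equal in the two arms. Here patient time is charged where resection adds visits and is not stated where resection might remove them. The protocol itself does not assume equal IVF use: its background puts forward avoided IVF as a possible benefit, and its analysis section allows for a difference by arm.

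What is at stake is the societal cost per extra live birth. It would carry the patient time of having surgery without the patient time saved, or added, through a change in fertility treatment.

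A second gap does not depend on IVF. Control women who go on to have resection are outside the patient cost questionnaire, so the same procedure carries a patient cost in one arm and none in the other.

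**Working it through.** **No figure to reproduce.** The protocol gives no visit counts, travel cost, productivity cost or IVF cycle numbers. The check is therefore a comparison of the text, followed by an illustration on stated assumptions.

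**1. What is costed**

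| Item | Treatment cost | Patient travel and time |
|---|---|---|
| Hysteroscopy, women randomised to resection | counted | counted |
| Resection in control women | hysteroscopy costs are in resource use | not collected |
| IVF/IUI, NHS-funded | counted | none stated |
| Privately funded fertility treatment | counted (societal analysis) | unclear |
| Antenatal and post-natal visits | counted | unclear |

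**2. The omitted term.** Let *d* be the fall in IVF cycles per woman with resection, *v* the visits per cycle and *c* the patient travel and time cost per visit. The planned incremental cost is too high by *d* × *v* × *c* per woman. Dividing by the difference in live birth rate gives the error in cost per extra live birth. Section 11.1 supplies that difference: 20% − 10% = 0.10. All other inputs are assumptions: *v* = 8, *c* = 50 to 100 currency units, *d* from −0.10 to 0.50.

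| *d* | *d* × 8 × *c*, per woman | Divided by 0.10, per extra live birth |
|---|---|---|
| −0.10 | −40 to −80 | −400 to −800 |
| 0 | 0 | 0 |
| 0.10 | 40 to 80 | 400 to 800 |
| 0.25 | 100 to 200 | 1,000 to 2,000 |
| 0.50 | 200 to 400 | 2,000 to 4,000 |

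The sign follows *d*, and nothing in the protocol fixes *d*.

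**3. Against the visits that are charged.** Assume 1 to 3 visits for hysteroscopy, 6 to 10 per IVF cycle, and equal cost per visit. The charged time is fully offset when *d* equals hysteroscopy visits divided by visits per cycle: from 1/10 = 0.10 to 3/6 = 0.50 cycles per woman.

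**4. Control women who have resection.** In Table 1, 10% to 50% of controls having resection before 6 months is amber, not red. With 1 to 3 visits each, the uncosted patient time is 0.10 × 1 = 0.1 to 0.50 × 3 = 1.5 visit-costs per control woman.

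**5. What the questionnaire could capture.** Three-month recall at 6, 15 and 24 months covers 9 of 24 months (37.5%). Table 2 separately records details of fertility treatments from medical notes at 6, 15 and 24 months.

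**The case against.** A reader might infer that the societal analysis cannot credit avoided IVF at all and is tilted against resection by design. The protocol does not support that. The savings in section 2.1 are savings to the NHS and to self-funding patients. Section 11.2 counts IVF/IUI treatment costs and privately funded treatment without restriction by arm. Nor is the direction given: section 11.2 says only that IVF may differ, and the statement in section 2.1 is conditional and concerns unexplained infertility. The trial also enrols women with known causes of infertility or recurrent miscarriage, and in both arms planned fertility treatment is to start or resume promptly (sections 6.1 and 6.2). These points stand, and they limit the finding to the travel and time component.

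Other arguments carry some weight:

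- **Wider reading of the sentence.** Patient-centred costs could govern the whole list, so that travel and time extend to private fertility treatment and to antenatal and post-natal visits. The repetition of antenatal visits, already listed under resource use, favours this. The hysteroscopy-only questionnaire and outcome 15 in section 8.3 count against it. Even on the wider reading, NHS-funded IVF, IUI and clinic visits remain without a patient time cost.
- **Antenatal visits.** On the narrow reading, antenatal travel and time are missing too, which favours resection if it raises births. With 0.10 extra births per woman and an assumed 8 to 10 visits each, 0.8 to 1.0 visit-costs per woman are left out. That compares with 0.10 × 8 = 0.8 for IVF at *d* = 0.10, so the net sign on that reading is open.
- **Randomisation during hysteroscopy.** In Pathway 2 (section 5.3) control women attend the same hysteroscopy, so resection adds fewer visits there.
- **Undesigned questionnaire.** The both-arm questionnaire, or the health economics analysis plan mentioned in section 7.2, could include these items. Neither is shown. The protocol does, however, state a boundary for patient costs and names an instrument that fits it, so this is more than detail left for later.

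**Conclusion.** The point holds in a limited form. As written, the societal analysis charges patient travel and lost work time for resection in the resection arm and states none for fertility-treatment visits in either arm, at least where these are NHS-funded. Only the patient travel and time part of a difference in fertility treatment is lost.

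Considering IVF visits alone, the error is against resection if resection lowers IVF use, nil if use is equal, and in favour of resection if use rises. The currency amounts above rest on assumed inputs and show only how the error scales; they are no estimate for this trial. The missing patient time for control women who have resection understates control-arm cost whatever happens to IVF use.

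The primary economic analysis and all clinical outcomes are unaffected. This is a correction worth making to a secondary analysis.

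**What to change.** 1. Apply one patient travel and time cost per visit or per cycle, in both arms, to the fertility treatments already recorded at 6, 15 and 24 months (Table 2).
2. Inform the per-visit value with a few items on travel, out-of-pocket cost and time off work in the both-arm resource use questionnaire. Because of the 3-month recall, use these items to set the unit value and take the visit or cycle count from the recorded treatments.
3. Apply the same hysteroscopy patient cost to control women who undergo resection.
4. State in section 11.2 whether patient travel and time are counted for antenatal and post-natal visits.
5. If steps 1 to 3 are not done, describe the analysis as the NHS and personal social services perspective plus selected patient costs, and do not call it societal.

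The cost is slight extra respondent burden, a little more costing work, and amended wording in section 11.2 and the health economics analysis plan.

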12.1 Trial Steering Committee

The role of the TSC is to provide supervision of the protocol, and statistical analysis plan, to provide advice on and monitor the study, to review information from other sources, consider recommendations from the DMEC and make recommendations on closing the trial prematurely. The TSC will meet at regular intervals, as defined in the TSC terms of reference. The TSC memberships includes an independent Chair, clinical and statistical expertise and PPI representation.

12.2 Data Monitoring and Ethics Committee

The DMEC will review monthly reports provided by the CTRU to assess the progress of the study, safety data, the critical endpoint data as required and will review the statistical analysis plan. The DMEC will meet at regular intervals, as defined by the DMEC charter and make recommendations to the TSC or funder, including whether the trial is stopped or modified on the basis of data / on safety grounds.

12.3 Trial Management Group

The trial will be supervised on a day-to-day basis by the Trial Management Group (TMG). This group reports to the TSC. At each participating centre a local Principal Investigator will report to the TMG via the staff at the Sheffield CTRU.

The core TMG will meet regularly at least once every two months but rising to at least once per month before key milestones (ethical approval, recruitment initiation etc.). In addition, investigator meetings will be set up during the recruitment phase of the study, at least once every two months, where the site PIs (or another delegated individual) will discuss pertinent issues with the research team, including recruitment, data completion and intervention delivery.

13. Data handling and record keeping

Participant confidentiality will be respected at all times during the study. Data will be collected and handled in line with CTRU Standard Operating Procedures and in accordance with NHS Trust policies at Sheffield Teaching Hospitals NHS Foundation Trust and at each participating site. This will ensure systems are in place to protect confidentiality of participants and the systems are secure.

Patients will be allocated a unique identification number that will be used to identify them throughout the trial. This will be recorded on all data collection forms to preserve pseudonymity

(except where identifiable information is collected, such as on the contact details form, which will be kept separately).

All consent forms and questionnaires will be kept in a locked filing cabinet in a secured area and will be retained for a minimum of 5 years after study completion, in accordance with the sponsor's archiving requirements.

Sheffield CTRU may request consent forms to be sent from the research site to the CTRU via post or email as part of remote monitoring procedures. Participants will be asked to consent to this in the study consent form.

Data will be entered on to a secure study database, hosted on University of Sheffield servers and accessible over the internet, which adheres to data protection and NHS regulations. Identifiable data, including names, addresses and dates of birth, will be shared with Sheffield CTRU to allow for participant follow-up. Consent will be obtained from the patient for this to occur.

13.1 Archiving

Data held by the CTRU will be stored in accordance with the archiving Standard Operating Procedure (*SOP PM012 Archiving*). Archived documents will be logged on a register which will also record items retrieved, by named individuals, from the archive. Electronic data will be stored in an 'archive' area of the secure CTRU server for the period stated above. Archiving of the site files and participants' records at each participating centre will be the responsibility of the local R&D Department.

14. Data access and quality assurance

Direct access to source data/documents (including hospital records/notes, clinical charts, laboratory reports, pharmacy records and test reports) will be granted to authorised representatives from CTRU (study manager, research assistant, data managers, lead & Senior Research Nurses), the sponsor and host organisations to permit study related monitoring, audits and inspections. Select CTRU staff will have access to personal data including names, addresses, phone numbers and email addresses in order to undertake the questionnaire follow-up. In addition to this, access to the eCRF and questionnaire data will be required for study monitoring and audit purposes. A study monitoring plan will be devised in accordance with the Sheffield CTRU SOPs on Trial Monitoring (QU001).

The study database resides on Sheffield CTRU's in-house data management system. All data transmissions are encrypted using SSL/TLS, and access to the system is controlled by usernames and encrypted passwords. A comprehensive privilege management feature can be used to ensure that users have access to only the minimum amount of data required to complete their tasks. This will be used to restrict access to personal identifiable data. The database will incorporate quality control procedures to validate the study data. Discrepancy reports will be generated to highlight missing and erroneous information.

Overall responsibility for ensuring that each participant's information is kept confidential will lie with the study sponsor. All paper documents will be stored securely and kept in compliance with the Data Protection Act (2018). Data entered onto the study database will be stored on CTRU servers at the University of Sheffield on behalf of the sponsors. After the trial has been completed and the reports published, access to the data will be strictly controlled.

14.1 Site assessment

Throughout this protocol, the trial 'site' refers to the hospital or clinic at which trial-related activities are conducted. Participating sites must be able to comply with:

- Trial treatments, imaging, clinical care, follow up schedules and all requirements of the trial protocol
- Requirements of the UK Policy Framework for Health and Social Care Research
- Data collection requirements

All site staff, including research staff, must be appropriately qualified by education, training and experience to perform the trial related duties allocated to them, which must be recorded on the site delegation log. CVs for all staff must be kept up to date, and copies held in the Investigator Site File (ISF), and the Trial Master File (TMF).

Before each site is activated, capability to conduct the trial will be assessed and documented. The CTRU will arrange a site initiation visit with each site or carry this out remotely. Site staff will be trained in the day-to-day management of the trial and essential documentation required for the trial will be checked. Once all the required documentation is in order and site staff have been trained, CTRU will formally activate the site to start recruitment. Sites should not open to recruitment until CTRU have provided this confirmation of activation.

14.2 Risk assessment

A risk assessment has been performed by the CTRU, in accordance with Sheffield CTRU Standard Operating Procedures.

Central and/or on-site monitoring (including Pharmacy if applicable) will be undertaken at a level appropriate to the detailed risk assessment and will be documented in the Site Monitoring Plan (SMP).

14.3 Reporting serious breaches and non-compliances

A “serious breach” is a breach of either: the conditions and principles of GCP in connection with the trial, or the protocol relating to the trial, which is likely to effect to a significant degree:

- the safety or physical or mental integrity of the participants of the trial; or
- the scientific value of the trial

The sponsor will be notified immediately of any case where the above definition may apply during the trial conduct phase. The sponsor of a clinical trial will notify the REC and, for CTIMPs, the MHRA in writing within 7 days of becoming aware of a serious breach.

All serious breaches and protocol non-compliances should be reported to CTRU, in-line with CTRU SOP PM011 and within 24 hours of site staff becoming aware.

14.4 On-site monitoring

On-site or remote monitoring will be performed according to the monitoring plan and in line with the Sheffield CTRU Site Monitoring SOP.

A site initiation visit will be performed either on-site or carried out remotely for each participating site before each site recruits their first participant. During this visit/remote contact, the Monitor will review with site staff the protocol, study requirements and their responsibilities to satisfy regulatory, ethical and Sponsor requirements.

Site monitoring may be performed either on site or remotely and will occur throughout the study as specified in the Site Monitoring Plan. Additional monitoring or on-site visits will be undertaken where required. During monitoring, the Monitor will review activity to verify that the:

1. Data are authentic, accurate and complete.
2. Safety and rights of the patient are being protected and
3. Study is conducted in accordance with the approved protocol and study agreements, GCP and all applicable regulatory requirements.

Accurate and reliable data collection will be assured by verification and cross-check of the eCRF against Investigator's records by the Study Monitor (source document verification) (see section 13 for further details on data collection). Study Monitor will contact and / or visit sites regularly to inspect CRFs throughout the study, to verify adherence to the protocol and completeness, consistency and accuracy of the data being entered on the CRFs.

A close-out review may be done remotely or by an on-site visit after the last patient last visit at each site. Further close-out activities may be carried out remotely after this time, up to database freeze.

